9.1.2 Outcomes for safety

9.1.2.1 Primary Outcome

The primary Outcome is the absolute and relative (%) frequency of patients with suspected adverse drug reactions (ADRs).

Safety will be assessed by use of the following other parameters of interest:

- Adverse events irrespective of seriousness
- Laboratory tests (if corresponding AEs are reported)

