9.5 STUDY SIZE

It is planned to enroll 360 patients with severe persistent asthma: 360 patients will initiate the Spiriva Respimat treatment, assuming 60 patients out of 360 patients will be dropped out without any data being collected.

The planned number of patients is not driven by a formal sample size calculation but is primarily based on the availability of patients eligible for Spiriva Respimat treatment.

300 patients will be registered for this study. The frequently observed ADR ($\geq 1.0\%$) in special use surveillance for Spiriva Respimat in patients with COPD was Coughing (1.2%). The frequently observed ADRs ($\geq 1.0\%$) in the clinical trial in Japanese patients with asthma were asthma (1.8%), dysphonia (1.8%) and dry mouth (1.8%). In the number of cases to be surveyed, it is evaluated if there is no possibility that the trend of incidence of these main adverse events would be largely increased compared to that of COPD patients.

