9.7.2 Safety analyses

The safety analysis will include all patients registered in the study and receiving the Spiriva Respimat treatment. In general, safety analyses will be descriptive in nature, will be based on BI standards, and will focus on ADRs related to the Spiriva Respimat treatment.

AEs will be coded using the current version of the Medical Dictionary for Regulatory Activities (MedDRA) and will be based on the concept of treatment emergent AEs. To this end, all AEs occurring between the first intake of Spiriva Respimat prescribed at baseline visit and within 30 days (inclusive) after the last intake will be considered 'treatment emergent'. An AE is considered to be ADR if either the physician who has reported the AE or the sponsor assesses its causal relationship as 'related'.

The frequency of AEs/ADRs will be tabulated by system organ class and preferred term for overall and for subgroups based on the important baseline characteristics.

No imputation is planned for missing AE data except for missing onset dates which will be handled according to BI standard.

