11. MANAGEMENT AND REPORTING OF ADVERSE EVENTS/ADVERSE REACTIONS

11.1 DEFINITIONS OF ADVERSE EVENTS

Adverse event

An adverse event (AE) is defined as any untoward medical occurrence, including an exacerbation of a pre-existing condition, in a patient in a study who received a pharmaceutical product. The event does not necessarily have to have a causal relationship with this treatment. An AE can therefore be any unfavourable and unintended sign (including an abnormal laboratory finding), symptom, or disease temporally associated with the use of a medicinal product, whether or not considered related to the medicinal product.

Adverse Drug Reaction (ADR)

A response to a medicinal product which is noxious and unintended.

Response in this context means that a causal relationship between a medicinal product and an adverse event is at least a reasonable possibility.

Adverse reactions may arise from use of the product within or outside the terms of the marketing authorisation or from occupational exposure. Conditions of use outside the marketing authorisation include off-label use, overdose, misuse, abuse and medication errors.

Serious adverse event

A serious adverse event - is defined as any AE which

- results in death,
- is immediately life-threatening,
- requires in-patient hospitalization, or
- prolongation of existing hospitalization
- results in persistent or significant disability or incapacity, or
- is a congenital anomaly / birth defect

Life-threatening in this context refers to a reaction in which the patient was at risk of death at the time of the reaction; it does not refer to a reaction that hypothetically might have caused death if more severe.

Medical and scientific judgement should be exercised in deciding whether other situations should be considered serious reactions, such as important medical events that might not be immediately life threatening or result in death or hospitalisation but might jeopardise the patient or might require intervention to prevent one of the other outcomes listed above. Examples of such events are intensive treatment in an emergency room or at home for allergic bronchospasm, blood dyscrasias or convulsions that do not result in hospitalisation or development of dependency or abuse. Any suspected transmission via a medicinal product of an infectious agent is also considered a serious adverse reaction.

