11.2 ADVERSE EVENT AND SERIOUS ADVERSE EVENT COLLECTION AND REPORTING

The investigator shall maintain and keep detailed records of all AEs in their patient files.

Collection and Reporting of AEs:

The study design is of non-interventional nature and the study is conducted within the conditions of the approved marketing authorisation. Sufficient data from controlled interventional trials are available to support the evidence on the safety and efficacy of the studied BI drug. For this reason the following AE collection and reporting requirements have been defined.

The following must be collected by the investigator in the (e)CRF via EDC system from first intake of Spiriva Respimat prescribed at baseline visit and within 30 days (inclusive) after the last intake:

- all ADRs (serious and non-serious) as soon as possible,
- all AEs with fatal outcome in patients exposed to Spiriva Respimat as soon as possible,
- all AEs which are relevant for a serious ADR or an AE with fatal outcome in patients exposed to Spiriva Respimat as soon as possible

All ADRs including those persisting after study completion must be followed up until they are resolved, have been sufficiently characterized, or no further information can be obtained.

The investigator carefully assesses whether an AE constitutes an ADR using the information below.

Causal relationship of adverse event:

The definition of an adverse reaction implies at least a reasonable possibility of a causal relationship between a suspected medicinal product and an adverse event. An adverse

reaction, in contrast to an adverse event, is characterised by the fact that a causal relationship between a medicinal product and an occurrence is suspected.

Medical judgment should be used to determine the relationship, considering all relevant factors, including pattern of reaction, temporal relationship, de-challenge or re-challenge, confounding factors such as concomitant medication, concomitant diseases and relevant history.

Arguments that may suggest **a reasonable causal relationship** could be:

- The event is **consistent with the known pharmacology** of the drug
- The event is known to be caused by or **attributed to the drug class**.
- A **plausible time to onset of the event** relative to the time of drug exposure.
- Evidence that the **event is reproducible** when the drug is re-introduced

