#### **4. CHANGES IN THE PLANNED ANALYSIS OF THE STUDY**

No change has been made in the planned analyses from the statistical methods described in the CTP.

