### **7.8.1 Adverse events**

Unless otherwise specified, the analyses of adverse events will be descriptive in nature. All analyses of AEs will be based on the number of patients with AEs and NOT on the number of AEs.

Furthermore, for analysis of AE attributes such as duration, severity, etc. multiple AE occurrence data on the CRF, will be collapsed into AE episodes provided that all of the following applies:

- The same MedDRA lowest level term was reported for the occurrences
- The occurrences were time-overlapping or time-adjacent (time-adjacency of 2 occurrences is given if the second occurrence started on the same day or on the day after the end of the first occurrence)
- Treatment did not change between the onset of the occurrences OR treatment changed between the onset of the occurrences, but no deterioration was observed for the later occurrence

For further details on summarization of AE data, please refer ([3](#), [4](#))

AE analyses will be carried out after integrating AE data from CRF and AE data from perceive system.

In addition, AEs coded as “no adverse event” will not be included in the AE analyses.

The analysis of adverse events will be based on the concept of treatment emergent adverse events. That means that all adverse events occurring between first drug intake till 30 days after last drug intake will be analysed. For details on the treatment definition, see [Section 6.1](#).

An overall summary of adverse events will be presented.

The frequency of patients with AEs, ADRs will be summarised by primary system organ class and preferred term. Also, the frequency of patients with ADRs will be summarised by primary system organ class, preferred term and the time to first onset date (1 to 30, 31 to 60, 61 to 90, 91 to 180, 181 to 365, >=366 days). Separate tables will be provided for patients with ADRs stratified by various patient subgroups defined in [Section 6.4](#), for patients with serious AEs. Subgroup analysis will display the frequency of patients, percentage (%) and odds ratio with 95%CI. Logistic regression will be used for odds ratio. The ‘unknown’ and ‘missing’ categories are excluded to calculate odds ratio. Patients with ‘priority survey items’ according to the drug’s Risk Management Plan will be summarised separately.

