An ADR is defined as an AE for which either the investigator or the sponsor (or both) assess the causal relationship to Spiriva Respimat either as “Possibility high”, “Possibility low” or “Unknown”. The system organ classes will be sorted according to the standard sort order specified by EMA, preferred terms will be sorted by frequency (within system organ class).

A serious AE is defined as an AE for which either the investigator or the sponsor (or both) assess the seriousness either as “Serious”.

The following AEs are detected on the basis of the Standardised MedDRA queries (SMQs) or Boehringer Ingelheim customised MedDRA query (BICMQ) (details are described in ADS plan).

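### Does counting adverse events with 'Unknown' causality as ADRs distort the primary safety outcome?

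*SAP*

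**What the plan says.** Protocol 9.1.2.1 sets the outcome: "The primary Outcome is the absolute and relative (%) frequency of patients with suspected adverse drug reactions (ADRs"). Protocol 9.7.2 gives the counting rule. An adverse event is an ADR "if either the physician who has reported the AE or the sponsor assesses its causal relationship as" *related*. Protocol 11.1 explains the concept: "Response in this context means that a causal relationship between a medicinal product and an adverse event is at least a reasonable possibility". The protocol offers no graded causality scale.

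SAP 7.4 refers the primary endpoint to SAP 7.8.1. There an ADR is an event for which the investigator, the sponsor or both "assess the causal relationship to Spiriva Respimat either as “Possibility high”, “Possibility low” or “Unknown". The same definition feeds the ADR tables by preferred term and by time to first onset, and the subgroup tables: "Subgroup analysis will display the frequency of patients, percentage (%) and odds ratio with 95%CI". SAP Section 4 states: "No change has been made in the planned analyses from the statistical methods described in the CTP".

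**The concern.** On its face, *Unknown* expresses neither relatedness nor a reasonable possibility of it. An event that one party rates as unrelated and the other as *Unknown* enters the primary numerator although neither has voiced a suspicion. If the protocol's *related* was meant to exclude *Unknown*, the SAP has widened the primary outcome while stating that nothing changed.

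The stake is the ADR percentage and every table built on it. Protocol 9.5 also wants to judge whether "the trend of incidence of these main adverse events would be largely increased compared to that of COPD patients", and a broader definition here than in the reference data would tilt that comparison upwards. *Possibility low* is not in dispute, since it fits the idea of a suspected reaction.

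**Working it through.** **Step 1: compare the two rules**

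| Element | Protocol | SAP 7.8.1 |
|---|---|---|
| Who decides | Physician or sponsor (9.7.2) | Investigator, sponsor or both |
| What counts | *Related* (9.7.2); suspected (9.1.2.1); at least a reasonable possibility (11.1) | *Possibility high*, *Possibility low*, *Unknown* |
| Scale defined | No | Names the categories that qualify |

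The either-party rule is unchanged. The only open element is whether *Unknown* belongs to *related*. SAP Section 3 describes the SAP as a more technical and detailed account of the protocol's analysis. Because the protocol supplies one word and no scale, a list of qualifying ratings is what such an account has to contain. Protocol 11.2 also lists arguments for concluding that there is no reasonable possibility of causation. An assessor who answers *Unknown* has not reached that conclusion.

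**Step 2: who could be affected**

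Let k be the number of patients whose only qualifying events are rated *Unknown*. The documents do not give k. Protocol 11.2 asks investigators to enter:

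- "all ADRs (serious and non-serious) as soon as possible". These were judged to be ADRs at entry, so the protocol would arguably count them anyway.
- Events relevant to a serious ADR. Such a patient already has an ADR.
- Fatal events and events relevant to them. These need no ADR judgement, so *Unknown* could bring in a patient here. Protocol Section 7 reports no deaths in the clinical programme.

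The pool is narrow but not provably empty. Protocol 9.1.2.1 and Annex 3 speak of adverse events generally, and SAP 7.8.1 merges event data from a second system.

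**Step 3: size for assumed k**

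Denominator: 360 planned − 60 without data = 300 (Protocol 9.5; the Abstract gives 300 as the safety set). Change in the primary percentage = 100 × k / 300.

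| k (assumed) | Added points | Base 15/300 (assumed) becomes |
|---|---|---|
| 0 | 0 | 5.0% |
| 1 | 0.33 | 16/300 = 5.3% |
| 3 | 1.00 | 18/300 = 6.0% |
| 5 | 1.67 | 20/300 = 6.7% |

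The exact (Clopper-Pearson) 95% interval for 15/300 is 2.8% to 8.1%, so every row lies inside it.

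**Step 4: single preferred terms**

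The asthma-trial rate of 1.8% in Protocol 9.5 corresponds to 0.018 × 300 = 5.4, or about 5 patients. One extra patient gives 6/5 = 1.2-fold, and three give 8/5 = 1.6-fold. The exact interval for 5/300 (1.7%) is 0.5% to 3.9%. The shifted values 6/300 = 2.0% and 8/300 = 2.7% stay inside it.

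**The case for a change.** The strongest contrary case is that this is the definition of the primary numerator, and a category meaning that no judgement could be made should not enter it without a stated link to the protocol's word. The final SAP is dated 1 October 2017, after the planned end of data collection on 31 August 2017, so a definition first visible then ought to be declared. The relative effect is larger at preferred-term level, where Protocol 9.5 makes its comparison. Reporting the ADR frequency with and without the *Unknown*-only patients would settle the question cheaply.

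Part of this stands. The wording is not linked, SAP Section 4 is silent, and one sentence saying that *Unknown* is treated as related would have been tidier. The link may exist in the company standards that Protocol 9.7.2 invokes, in the case report form, or in the references that SAP 7.8.1 cites for summarising adverse events. None of these can be read here, so its absence from the public text is weak evidence that it is missing.

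The rest does not carry. Nothing suggests that the choice was driven by the data. A second set of ADR figures would correct no result. It would not secure the comparison with COPD either, because the documents do not say which causality definition lies behind those reference rates. By preferred term it would mostly add sparse rows.

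**Conclusion.** The mismatch in wording is real, but it is a documentation gap and not a demonstrated error. Analysts who follow SAP 7.8.1 obtain one explicit, reproducible ADR frequency, and a reader of the SAP can see which ratings qualify. The rule errs on the side of counting more reactions, and the analysis is descriptive, so no error rate is touched.

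The possible effect is 0.33 percentage points per affected patient among 300. The number affected is unknown, may be zero, and is limited by what Protocol 11.2 asks investigators to collect. The illustrations rest on assumed counts (k up to 5, and bases of 15 and 5 patients), and under them the shift stays within sampling error. The conclusion rests on reading SAP 7.8.1 as the translation of *related* into recorded categories. If the sponsor had meant *related* to exclude *Unknown*, the count would be wider than intended by those k patients, in the cautious direction. No change to the plan follows.

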#### **7.8.2      Laboratory data**

Not applicable. Only clinically relevant findings reported as AE will be analysed as a part of AE analyses.

#### **7.8.3      Vital signs**

Only clinically relevant findings reported as AE will be analysed as a part of AE analyses.

#### **7.8.4      ECG**

[figure not shown]
Not applicable. Only clinically relevant findings reported as AE will be analysed as a part of AE analyses.

#### **7.8.5      Others**

No plan for other safety parameters.

## 10. HISTORY TABLE

Table 10: 1 History table

Version	Date (DD-Mmm-YY)	Author	Sections changed	Brief description of change
Final	01-Oct-2017		None	This is the final TSAP without any modification

